#### **4.4 Purpose and timing of interim analyses**

Please refer to [Section 12.7](#).

#### **4.5 Risks and benefits**

Detailed descriptions of the expected safety, tolerability and efficacy characteristics of each of the proposed individual treatment arms can be found in [Section 17](#).

Commercially Confidential Information

---

Commercially Confidential Information

Based on CCI risk considerations, additional safety measures employed in NEXSCOT include, but are not limited to:

- The study employs safety management measures which are considered relevant and appropriate for this patient population and protocol to facilitate safe conduct of the study.
- The study will only be conducted by investigators who have broad experience with patients who have multiple metabolic and/or liver comorbidities.
- Patients with advanced liver disease, for example cirrhosis or more severe hepatitis, will not be enrolled.
- Patients with evidence of ECG abnormalities consistent with significant cardiovascular risk will not be enrolled.
- Participants will have a visit every two weeks during the first two months of treatment for safety assessments, including ECGs and laboratory tests. Halfway through the final month of treatment (Month 3), study staff will contact the participant by phone to inquire about tolerability and safety.
- This protocol pre-specifies both liver and renal events requiring intervention ([Section 16.1](#) and [Section 16.2](#), respectively).
- The study will be also monitored by an internal Safety Assessment Committee (SAC), which will provide an additional layer of oversight for safety events. For further details, please refer to [Section 10.2.1](#) and the standalone Safety Surveillance Plan (SSP).
- Appropriate eligibility criteria and specific dose modification and stopping rules are included in this protocol. The risk to subjects in this trial will be minimized by compliance with the eligibility criteria and study procedures, as well as close clinical monitoring.

## Benefits

The key, potential benefits expected to be associated with participation in the NEXSCOT protocol include:

1. Participants will receive a potentially efficacious treatment where currently no approved treatment is available. Over the duration of the study, patients may have the clinical benefit of reductions in hepatic fat, inflammation and/or the ongoing fibrotic process.
2. The severity of the participant's NAFLD will be staged by liver fat, ELF Test and liver transaminases. Knowledge of these parameters may guide future treatment and behavior modification for the particular participant.
3. Participants will contribute to the potential identification of high efficacy, combination regimens for NASH treatment, where an unmet medical need exists.

## Benefit:risk associated with the COVID-19 pandemic

The assessment of the benefit:risk for the study in the context of the COVID-19 pandemic concluded the absence of additional risks for the study population and/or related to the investigational medicinal product. As the COVID-19 situation evolves, investigators must use their best judgment to minimize risk to participants during the conduct of the study.

### 4.5.1 Blood sample volume

A volume of approximately 625 mL is planned to be collected over a period of up to approximately seven to eight months from each participant as part of the study. Additional samples may be required for safety monitoring.

Timings of blood sample collection are outlined in the Assessment schedule ([Table 8-1](#)).

A summary blood log is provided in the Site Operations Manual (SOM). Instructions for all sample collection, processing, storage and shipment information is also available in the SOM and the central laboratory manual.

See [Section 8.5.4.1](#) on the potential use of residual samples.

### 4.6 Rationale for public health emergency mitigation procedures

Remote procedures are planned in this study to minimize burden on participants, and offer them increased flexibility to participate in the study from a remote location (as described in [Section 3](#) and defined in [Section 8](#)). During a public health emergency as declared by local or regional authorities (e.g., pandemic, epidemic, natural disaster), additional mitigation procedures to ensure participant safety and trial integrity may be considered. Notification of the public health emergency should be discussed with Novartis prior to implementation of mitigation procedures, and permitted/approved by local or regional Health Authorities and Ethics Committees as appropriate.

## 5 Population

The study population will be comprised of male and female NAFLD patients with a NASH-like biomarker phenotype.

Approximately 25 participants per arm will be enrolled in the study, and around 20 participants per arm are expected to be evaluable. Based on the results of the ongoing data review, the sample size may be increased to an enrollment target up to approximately 50 total for a specific arm; for example, due to higher than anticipated variability of the biomarker data.

Please refer to [Section 17](#) (cohort-specific information) for eligibility criteria specific to each treatment arm.

The investigator must ensure that all participants enrolled into the study meet the following eligibility criteria. No additional criteria should be applied by the investigator, in order for the study population to be representative of all eligible patients.

Participant selection is to be established by checking through all eligibility criteria at both screening and baseline, unless otherwise specified. Please also refer to the [Assessment Schedule](#) for the exact tests to be performed at either visit, but note that certain eligibility criteria may only need to be confirmed to be within the ranges specified at one of the two visits. A relevant record (e.g., checklist) of the eligibility criteria must be stored with the source documentation at the study site.

Deviation from any entry criterion excludes a participant from enrollment/randomization into the study.

Reference ranges for laboratory assessments are located in the standalone laboratory manual.

If any parameters are found to be outside of the range specified in the inclusion or exclusion criteria (where relevant) at screening or baseline, the assessment can be repeated once to rule-out laboratory error or anomaly.

Refer to [Section 8.1](#) (Screening) for information regarding re-screening.

## 5.1 Inclusion criteria

Participants eligible for inclusion in this study must meet **all** of the following criteria:

1. Signed informed consent(s) must be obtained prior to participation in the study.
2. Male and female participants 18 years or older (at the time of the screening visit).
3. NAFLD patients with a NASH-like biomarker phenotype are defined based on the presence of **ALL FIVE** of the following:
  - a. ALT  $\geq$  43 IU/L (males) or  $\geq$  28 IU/L (females)\* **AND**
  - b. BMI  $\geq$  27 kg/m^2 (in participants with a self-identified race other than Asian) or  $\geq$  23 kg/m^2 (in participants with a self-identified Asian race) **AND**
  - c. History of Type 2 diabetes mellitus with HbA1c  $\leq$  9% at baseline **AND**
  - d. ELF Test score  $\geq$  8.5 and  $\leq$  10.5 at either screening or baseline **AND**
  - e. Liver fat  $\geq$  8% at baseline as determined by the reading of the central MRI laboratory of locally produced images. The MRI assessment should only be performed after eligibility has been confirmed from all other baseline assessments.
4. Participants must weigh at least 40 kg (88 lbs.) and no more than 150 kg (330 lbs.).
5. Able to communicate well with the investigator, to understand and comply with the requirements of the study.

\*Average of two independent results obtained approximately four weeks apart (e.g., once at screening and once at baseline) must be in this range AND both results must be within 30% of one another. Should the initial variance between the two baseline measures be > 30%, a third measure may be obtained 2 weeks after the second measurement. Such participants would be eligible for enrollment provided the variability between any two of these three samples is  $\leq$  30%.

## 5.2 Exclusion criteria

### IMPORTANT

The exclusion criteria for the core protocol are located in this section ([Section 5.2](#)). These exclusion criteria apply to all participants enrolled into this study. However, there may also be additional treatment specific exclusion criteria which are provided in [Section 17](#) for the individual treatment arms.

Participants meeting any of the following criteria and any criteria detailed in the cohort-specific information ([Section 17](#)) are not eligible for inclusion in this study.

1. History of hypersensitivity to any of the study treatments or excipients or to drugs of similar chemical classes.
2. Use of other investigational drugs within 5 half-lives of randomization, or within 3 months, whichever is longer; or longer if required by local regulations.
3. Use of obeticholic acid (OCA) within 1 month of randomization.
4. Participants on treatment with the following medicines UNLESS they are on stable dosing for at least 3 months before randomization: anti-diabetic medications, insulin, beta-blockers, thiazide diuretics, fibrates, statins, niacin, ezetimibe, thyroid hormone, psychotropic medications, estrogen or estrogen containing birth control.
5. Participants on treatment with vitamin E at doses  $>$  200 IU/day and  $\leq$  800 IU/day UNLESS they are on stable dosing for at least 6 months before randomization, OR any participants on treatment with vitamin E  $>$  800 IU/day regardless of stable dosing.
6. Use of pharmacologically-active weight loss drugs such as lorcaserin, phentermine/topiramate, bupropion-naltrexone HCl, or orlistat within 1 month of randomization.
7. Use of strong inhibitors of CYP3A4/5 (for example; boceprevir, clarithromycin, conivaptan, grapefruit juice, indinavir, itraconazole, ketoconazole, lopinavir, fazodone, nelfinavir, posaconazole, ritonavir, saquinavir, telaprevir, telithromycin, and voriconazole) within 5 half-lives or 7 days of randomization, whichever is longer.
8. Use of strong CYP3A inducers (for example; avasimibe, carbamazepine, phenytoin, rifampin, St. John's wort) within 5 half-lives or 7 days of randomization, whichever is longer.
9. Participants taking medications prohibited by the protocol, including cohort-specific guidance. See the 'Prohibited Treatment' sections in the core ([Section 6.2.2](#)) and cohort-specific portions ([Section 17](#)) of the protocol for further details.
10. History of malignancy for which, based on the investigator assessment, would be reasonable grounds for exclusion.

11. Pregnant or nursing (lactating) women, where pregnancy is defined as the state of a female after conception and until the termination of gestation, confirmed by a positive hCG laboratory test.
12. Women of child-bearing potential, defined as all women physiologically capable of becoming pregnant, **unless** they are using highly effective methods of contraception during dosing and for a duration equal to approximately 5 times the terminal half-life after stopping study medication. Highly effective contraception methods include:
  - Total abstinence (when this is in line with the preferred and usual lifestyle of the participant). Periodic abstinence (e.g., calendar, ovulation, symptothermal, post-ovulation methods) and withdrawal are not acceptable methods of contraception;
  - Female sterilization (have had surgical bilateral oophorectomy with or without hysterectomy), total hysterectomy, or tubal ligation at least six weeks before taking study treatment. In case of oophorectomy alone, only when the reproductive status of the woman has been confirmed by follow up hormone level assessment;
  - Male sterilization (at least 6 months prior to screening). For female participants on the study, the vasectomized male partner should be the sole partner for that participant;
  - Use of oral (estrogen and progesterone), injected, or implanted hormonal methods of contraception, or placement of an intrauterine device (IUD) or intrauterine system (IUS), or other forms of hormonal contraception that have comparable efficacy (failure rate <1%), for example, hormone vaginal ring or transdermal hormone contraception.

In case of use of oral contraception women should have been stable on the same pill for a minimum of 3 months before taking study treatment.

If local regulations deviate from the contraception methods listed above to prevent pregnancy, local regulations apply and will be described in the ICF.

Women are considered post-menopausal if they have had 12 months of natural (spontaneous) amenorrhea with an appropriate clinical profile (e.g., age appropriate history of vasomotor symptoms). Women are considered not of child bearing potential if they are post-menopausal or have had surgical bilateral oophorectomy (with or without hysterectomy), total hysterectomy, or tubal ligation at least six weeks ago. In the case of oophorectomy alone, only when the reproductive status of the woman has been confirmed by follow up hormone level assessment is she considered not of child bearing potential.

13. Sexually active males will be excluded UNLESS they agree to use a condom during intercourse while taking study medication and for a duration equal to approximately 5 times the terminal half-life after stopping study medication, and should not father a child in this period. A condom is required to be used also by vasectomized men in order to prevent delivery of the drug via seminal fluid. In addition, male participants must not donate sperm for the time period specified above. If local regulations deviate from the contraception methods listed above to prevent pregnancy, local regulations apply and will be described in the ICF.
14. Current or history of significant alcohol consumption for a period of more than 3 consecutive months within 1 year prior to screening. Significant alcohol consumption is defined as  $\geq 21$  units of alcohol per week in males and  $\geq 14$  units of alcohol per week in

females; a unit of alcohol is equivalent to 8 grams pure ethanol, 12 ounce (355 mL) beer, 4 ounce (118 mL) glass of wine, or 1 ounce (30 mL) shot of hard liquor.

15. Inability to reliably quantify alcohol consumption based upon local study physician judgment.
16. History of ongoing drug abuse within the 12 months prior to dosing.
17. Prior or planned (during the study period) bariatric surgery (e.g., gastroplasty, roux-en-Y gastric bypass).
18. Type I diabetes or uncontrolled Type II diabetes (defined as HbA1c > 9% at baseline).
19. Evidence of severe acute or chronic renal insufficiency, such as participants with eGFR < 60 mL/min/1.73m^2.
20. Suspected or confirmed Gilbert's syndrome.
21. Evidence of hepatic decompensation or severe liver impairment or cirrhosis, as defined by the presence of any of the following abnormalities (reminder that all lab ranges below must be confirmed at both screening and baseline):
  - Serum albumin < 3.2 g/dL
  - INR > ULN
  - Total bilirubin > ULN
  - ALT or AST > 5x ULN\*
  - Alkaline phosphatase > ULN
  - Platelets outside of normal reference range
  - History of esophageal varices, ascites, or hepatic encephalopathy
  - Splenomegaly

\*Average of two independent results obtained approximately four weeks apart (e.g., once at screening and once at baseline) in this range AND both results within 30% of one another. Should the initial variance between the two baseline measures be > 30%, a third measure may be obtained 2 weeks after the second measurement. Since this is an exclusion criterion, in order for the participant to qualify, he/she must demonstrate an average ALT and AST  $\leq$  5x ULN where the two individual measurements are  $\leq$  30% variable from one another.

22. History or presence of other concomitant liver diseases including, but not limited to:
  - Hepatitis B or C virus (HCV, HBV) infection, confirmed using standard laboratory assays. Participants with a history of HCV who have appropriate documentation of curative therapy per Investigator's discretion (e.g., biopsy, sustained virologic response [SVR] for more than 3 years prior to screening) are not excluded.
  - Primary biliary cholangitis (PBC)
  - Primary sclerosing cholangitis (PSC)
  - Alcoholic liver disease
  - Definite autoimmune liver disease or overlap hepatitis
  - Hemochromatosis
  - Known bile duct obstruction
  - Suspected or proven liver cancer
23. History of liver transplantation or current placement on a liver transplant list.

24. Known positivity for Human Immunodeficiency Virus (HIV) infection, confirmed using standard laboratory assays.
25. History of non-adherence to medical regimens, or participants who are considered by the investigator to be unable to reliably comply with the requirements of the study.
26. History or current diagnosis of ECG abnormalities indicating safety concerns for participants such as:
  - Concomitant clinically significant cardiac arrhythmias, e.g., sustained ventricular tachycardia, and clinically significant second or third degree AV block without a pacemaker
  - History of familial long QT syndrome or known family history of Torsades de Pointes
27. Donation or loss of 400 mL or more of blood within eight (8) weeks prior to initial dosing, or longer if required by local regulation.
28. Participants with contraindications to MRI imaging, including but not limited to:
  - Brain aneurysm clip
  - Implanted neural stimulator
  - Implanted cardiac pacemaker or defibrillator, or presence of intracardiac wires
  - Prosthetic heart valves
  - Cochlear implant
  - Ocular foreign bodies that might be ferromagnetic (e.g., metal shavings)
  - Other implanted medical devices (e.g., insulin pumps)
  - Metal shrapnel or bullets still in the body
  - Severe claustrophobia
  - Piercings or tattoos (as determined by the investigator and imager)
  - Weight in excess of MRI machine capacity
29. Signs or symptoms, in the judgment of the investigator, of a clinically significant systemic viral, bacterial or fungal infection within 30 days prior to screening.
  - COVID-19 specific: It is highly recommended that PCR or antigen testing for COVID-19 be completed within 1 week prior to first dosing. If testing is performed, a positive test result would exclude a participant from enrollment into the study. Additional testing may occur at the discretion of the investigating physician. COVID-19 testing should be completed via nasal or throat swabs if available. If testing is not performed, the investigator must document their discussion with the subject regarding testing, and the rationale for not testing, in the source documentation. This requirement may be ignored if the pandemic is declared ended by the country where the site is located, and resumed if the pandemic recurs.

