### 3 Study design

This is a non-confirmatory, multicenter, open label, platform study in NAFLD patients with a NASH-like biomarker phenotype.

Commercially Confidential Information

There is a maximum of five cohorts planned. Each cohort will consist of a 33-day screening period (Day -60 to Day -28), a baseline period of 27 days (Day -27 to Day -1), a treatment period of 12 weeks (Day 1 to Day 85), and a study completion evaluation (End of Study [EOS] 1) approximately 28 days after the last drug administration (Day 113).

Commercially Confidential Information

Participants will be advised to maintain their recommended diet for NAFLD during the study. The study design scheme is shown below in [Figure 3-1](#):

**Figure 3-1** Study design

EOS = End of Study

ARandomization for any patient can occur after informed consent is obtained and eligibility is confirmed, ideally as close to Day 1 as possible. Patients will be randomized into any of the treatment arms open to enrolment for which the patient meets the eligibility criteria.

BTreatment arm(s) will be defined for each cohort.

CEOS2 visit only required for treatments with an extended half-life. For all other treatments, EOS1 will serve as the EOS visit.

Participants who meet the eligibility criteria at screening will have baseline assessments performed, including determination of the percent liver fat content by MRI.

Once eligibility has been confirmed from screening and baseline assessments, participants will be randomized into any of the treatment arms open to enrollment for which the participant meets the eligibility criteria using an Interactive Response Technology (IRT) system. If a participant does not meet the specific eligibility criteria of a particular treatment arm, the participant will be randomized to any open and actively enrolling arms for which the participant is eligible. Randomization will be stratified by race and BMI (refer to [Section 6.3.2](#)). In the event that there

is only one open treatment arm in a cohort or if participants are only deemed eligible for one treatment arm, participants will be enrolled using the same IRT system, but without randomization.

The first dose of study medications will be administered to participants during the visit on Day 1, and scheduled assessments will be performed as defined in the [Assessment schedule](#).

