#### **Baseline definition:**

Baseline for ALT is defined as the mean of the last 2 non-missing measurements taken prior to the first dose of study drug administered at the Day 1 visit.

For all other secondary efficacy endpoints, baseline is defined as the last non-missing measurement prior to the first dose of study drug administered at the Day 1 visit.

All assessments (scheduled and unscheduled) will be considered into the derivation of the baseline.

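### Apart from an optional COVID-19 test, exclusion 29's infection window closes 28 to 60 days before first dose, so an active systemic infection at Day 1 does not exclude

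*Protocol*

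**What the plan says.** Exclusion 29 in Protocol 5.2 has two parts. The general part covers signs or symptoms, in the investigator's judgment, of a "clinically significant systemic viral, bacterial or fungal infection within 30 days prior to screening". The COVID-19 part recommends that "PCR or antigen testing for COVID-19 be completed within 1 week prior to first dosing" and adds: "If testing is performed, a positive test result would exclude a participant from enrollment into the study". A site may skip the test if it documents why, and the requirement may be ignored once the country declares the pandemic ended.

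Protocol section 3 sets out a "33-day screening period (Day -60 to Day -28), a baseline period of 27 days (Day -27 to Day -1", with the first dose on Day 1. Protocol section 5 establishes eligibility by "checking through all eligibility criteria at both screening and baseline, unless otherwise specified", and tells investigators to add no criteria of their own.

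On the analysis side, SAP 6.2.1 states: "Baseline for ALT is defined as the mean of the last 2 non-missing measurements taken prior to the first dose". It continues: "For all other secondary efficacy endpoints, baseline is defined as the last non-missing measurement prior to the first dose". In Table 8-1 the central biomarkers are drawn at Baseline and Day 1, with only ELF drawn at Screening, so the hsCRP baseline is normally the Day 1 value. SAP 6.2.3 analyses hsCRP as a log ratio to baseline and gives a least squares mean, 80% confidence interval and p-value for each treatment at each visit.

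**The concern.** An infection criterion would be expected to describe the participant's state when study drug starts. This one describes the month before the screening visit. Checking it again at baseline does not help, because a window defined backwards from screening does not move. An investigator who sees a febrile bacterial illness a few days before Day 1 has no infection criterion to apply, and section 5 bars adding one. Criteria 16 (drug abuse) and 27 (blood loss) are tied to dosing, as is the COVID-19 clause, so the general clause is out of step with its neighbours.

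The secondary issue is measurement. hsCRP is an acute-phase marker and its baseline rests on one value, with no stability check and no eligibility range that would trigger a repeat. Nothing in the visible SAP sets aside a value taken during an infection. With about 20 evaluable participants per arm, one or two such values can move a per-arm estimate noticeably.

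**Working it through.** **1. The gap.** With no Day 0, screening lasts -28 - (-60) + 1 = 33 days and baseline -1 - (-27) + 1 = 27 days. This reproduces the protocol's figures and totals 60 days. From the screening visit to Day 1 is therefore 28 days (screened on Day -28) to 60 days (screened on Day -60). The general clause looks at days 28–58 before dosing in the first case and 60–90 in the second. A COVID-19 test, if done, covers at most the last 7 days for one infection, leaving 28 - 7 = 21 to 60 - 7 = 53 days open even for COVID-19. No other criterion in 5.2 covers an acute infection arising after screening; 22 and 24 concern hepatitis B and C and HIV.

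**2. Inputs for hsCRP.** From the protocol: n = 20 evaluable per arm. The documents give no infection rate, marker response or hsCRP variance, so these are assumed: point prevalence p of 2% to 5%, a rise of f = 10-fold (3-fold as a milder case), and on the log scale a between-person SD of 0.9 and a within-person SD of 0.55.

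**3. If infections sat only at baseline.** With k of n baselines inflated f-fold, the per-arm geometric mean ratio is f^(-k/n).
- 10-fold: one participant gives 10^(-1/20) = 0.891; two give 10^(-2/20) = 0.794.
- 3-fold: 3^(-1/20) = 0.947 and 3^(-2/20) = 0.896.
- Chance of at least one affected in 20: 1 - 0.98^20 = 0.33 at 2%, 1 - 0.95^20 = 0.64 at 5%. Chance of two or more: 0.06 and 0.26.

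In a simulation of two arms of 20, adjusted for log baseline, the 80% interval lay wholly below no change in about 0.11 of trials with nobody affected. This became about 0.25 with one 10-fold baseline in each arm and about 0.45 with two. These figures are conditional on infections occurring before dosing and never afterwards.

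**4. If infections occur at both times.** The expected log ratio shifts by (p_post - p_base) × ln f, so the ratio is multiplied by f^(p_post - p_base). With equal prevalence this is 10^0 = 1. The same simulation agrees:

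| Prevalence, baseline and on treatment | Per-arm ratio | P(80% CI below 1) |
|---|---|---|
| none | 0.999 | 0.111 |
| 2% | 0.998 | 0.116 |
| 5% | 0.997 | 0.124 |

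**5. What remains is noise.** Inflated baselines add p(1-p)(ln 10)² to the variance of a log ratio: 0.0196 × 5.30 = 0.104 at 2%, 0.0475 × 5.30 = 0.252 at 5%. Against 2 × 0.55² = 0.605, and before baseline adjustment, the standard error with n = 20 goes from √(0.605/20) = 0.174 to √(0.709/20) = 0.188 or √(0.857/20) = 0.207. That is 8% or 19% wider.

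**6. Removing pre-dose infections only.** Then p_base = 0 and the ratio becomes 10^0.02 = 1.05 or 10^0.05 = 1.12, a false rise. In simulation the 80% interval lay wholly above 1 in 0.15 and 0.24 of trials.

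**7. ALT and ELF (assumed inflation of one participant's baseline).** For ALT, a 1.3-fold or 1.5-fold inflation of the averaged baseline gives 1.3^(-1/20) - 1 = -1.3% or 1.5^(-1/20) - 1 = -2.0%, against the 30% benchmark in Protocol 4.1.3. For ELF, a 0.5-unit inflation gives 0.5/20 = 0.025 units, against 0.3.

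**The case against.** A reader might infer that the recovery of infected participants would be reported as an anti-inflammatory drug effect, since there is no concurrent placebo and each arm gets its own interval and p-value. The documents do not support that. Nothing in them suggests that infections cluster before dosing, and the visible SAP leaves on-treatment hsCRP values during infection in the analysis just as it leaves baseline ones. With equal rates the two cancel in expectation (step 4). The Cohort 1 contrast is randomized 1:1, so it is also unbiased in expectation; chance imbalance adds noise. Participants enrolled without randomization (Protocol 6.3.2) lack that protection.

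Other points in the plan's favour also stand. Only illness near Day 1 affects hsCRP, because the last pre-dose value is used. ALT has an averaged baseline and a 30% agreement rule at entry, although that rule is applied, for example, to screening and baseline values, so the Day 1 ALT may escape it. Protocol 4.1.3 names ALT, liver fat and ELF as the evidence of efficacy, not hsCRP, and the trial is non-confirmatory.

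On safety, physical examination, vital signs and haematology are scheduled at Baseline and Day 1, and Protocol 9.1.1 requires study treatment to stop where participation poses a safety risk. So an ill participant would probably be noticed. These provisions soften the gap but do not close it, because none of them is an entry criterion for infection at first dose.

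**Conclusion.** The gap in the wording is certain and needs no assumption: the general infection clause stops 28 to 60 days before first dose, and the only later cover is one optional test for one infection. Its main consequence is that the criterion does not do its job when dosing starts.

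The statistical consequence is secondary and confined mainly to hsCRP: extra noise in a single-value baseline, about 8% to 19% on the unadjusted standard error under the assumed 10-fold rise and 2% to 5% prevalence. A systematic false fall would require infections to be more common at baseline than on treatment, which the documents do not indicate. The illustrated shifts in ALT and ELF are small against the protocol's own benchmarks.

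**What to change.** In Protocol 5.2, reconcile the general clause of exclusion 29 with its COVID-19 clause so that the infection window runs up to first dose. Where an infection appears after screening, the single re-screen allowed in Protocol 8.1 is available, subject to the sponsor's agreement. What counts as clinically significant stays with the investigator, as now.

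In SAP 6.2.3, add a sensitivity analysis of hsCRP that omits values taken during an infection adverse event at any visit, pre-dose and on treatment alike. Omitting only the pre-dose ones would introduce the upward bias in step 6. The symmetric analysis matters more once the entry window is extended, because on-treatment infections would otherwise remain unopposed.

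The cost is a phrase in the protocol, one derived flag and one extra table. Adverse events are recorded from informed consent (Protocol 10.1.1), so no new data are needed. The downside is that a few participants start later or are re-screened.
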